#### **D. Treatment Randomization**

Subjects will be randomized 1:1 to a treatment sequence via an electronic system using a permuted-block schedule stratified by investigational site. Subjects will be randomized to receive either MIR RBCs followed by REF RBCs, or to receive REF RBCs followed by MIR RBCs.

#### **E. Assessment Schedule**

Patients will undergo a Screening Period, Treatment Assessments and End of Study Assessments. Please see Table 14-1 in Clinical Investigation Plan for a detailed Study schedule, including all measurements and evaluations for the entire study period (Screening to Follow-up) presented in tabular form.

During the Screening period (days -28 to 0), each patient will be screened to determine the eligibility.

If screening procedures confirm eligibility, the subject will be randomized within 10 days prior to initiation of the first study transfusion (Study Day 0).

During Treatment Phase, eligible patients will be followed by 2 transfusion episodes for assessment schedules specified in Table 14-1.

With Each RBC Transfusion Episode:

At Baseline the Investigator will identify and document the target post-transfusion (15 min) Hb level; with each transfusion episode, the Investigator will perform the following:

1. Calculate the volume of RBCs required to achieve the target Hb (identified at baseline)
  - a. 
$$[(\text{desired hemoglobin}) - (\text{current hemoglobin})] \times (\text{body weight [kg]}) \times (3/\text{Hct of RBC units}) = \text{mL to transfuse}$$

Note: 3 is constant in the formula above

2. If the post-transfusion (15 min) Hb is under 15% of the target Hb, then an additional transfusion should be considered. If the post-transfusion Hb is over 15% of the target Hb, this will be documented.

The schedule will continue with the 50-day wash-in that serves to ensure that an adequate volume of RBCs from the assigned treatment allocation (MIR RBCs

versus REF RBCs) have been transfused into the subject prior to collecting samples to support the primary endpoint.

All patients who come off study should have an end of study treatment follow-up visit that will occur 2-4 weeks after the last per protocol transfusion. A final study visit will occur at least 60 days after the last per protocol transfusion.

## **V. Interventions**

### **A. Clinical Trial Material**

The RBCs to be utilized in this study will be as follows and will meet standard release criteria for transfusion.

- MIR RBCs: RBCs will be derived from WB collected in citrate phosphate dextrose (CPD) solution, treated with the Mirasol System for WB, LR, and stored in Additive Solution Formula 3 (AS-3) for  $\leq$  21 days at 1 - 6°C.
- REF RBCs: LR apheresis RBCs or WB-derived RBCs will be per site standard inventory.

No other pathogen reduction treated blood products including platelets and/or plasma may be used for transfusion in subjects during study participation.

## **VI. General Analytical Considerations**

### **A. Study Time Points**

#### Baseline

Baseline for analysis purposes is defined as the last assessment prior to treatment start date/time (or randomization date, for patients who never receive any treatment) for each treatment period. In cases where the date is the same and the times are unknown, assessments taken on the same day are considered baseline.

#### Study Day

Study day for analysis purposes is defined as (date of event – treatment start date) (+ 1 if the event occurs after treatment start date) within each period.

#### Treatment Start Date

Treatment start date is defined within each period as the date of the first transfusion received for each period.

## **B. Missing Data**

In general, missing data will not be imputed. Missing values will generally be kept as missing in the data analyses. However, imputations will be made in the following cases described below:

Imputations will be made for partial dates and the relationship of an Adverse Event (AE) to the study agent. These imputations are explained in more detail below.

For partial dates, other than the start date of an AE, the following conventions will be used for dates if needed:

- For dates missing both the month and the day, the month will be imputed to 7 and the day will be imputed to 15.
- For dates missing only the day where the month and year correspond to the first day of dosing the day will be imputed to the first day of dosing. All other missing days will be imputed to 15.
- For dates missing the year, no imputation will be used.

For partial onset dates for AE, the following conventions will be used:

- For dates missing both the month and the day, if the year corresponds to the year of first dose, the date will be imputed as the same as the date of first dose. Otherwise, the month will be imputed to 7 and the day will be imputed to 15.
- For dates missing only the day where the month and year correspond to the first day of dosing the day will be imputed to the first day of dosing. All other missing days will be imputed to 15.
- For dates missing the year, no imputation will be used.

Missing severities of AEs will not be imputed and will be considered missing in any tabulations of AE severity. If an AE is missing a response to the question regarding relationship to study treatment, or relationship to study procedure, or relationship to study procedure, the event will be considered to be related.

The normalized Hb AUC is expected to be calculated using four timepoints: the 15-minute post transfusion, 24-hour, Day 7, and end of transfusion interval (ie, pre-transfusion measure for the subsequent interval). If either the 24-hour or Day 7 measure is missing, the AUC will still be calculated using the rules described below in Section VIII.A. If both are missing, or if either the 15-minute post transfusion or the end of transfusion interval are missing, then no AUC will be calculated for that interval.

As a sensitivity analysis to the primary analysis, multiple imputation will be used to estimate missing normalized Hb AUC. Further details are provided in Section VIII.B.

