## IV. Study Design

### A. Design Overview

This is a prospective, multi-center, randomized, crossover trial to evaluate the clinical effectiveness of RBCs derived from Mirasol-treated WB (MIR RBCs) versus conventional RBCs (REF RBCs) in transfusion dependent thalassemia patients. Throughout the clinical trial, RBC transfusion volume and frequency will be determined by each subject's treating physician.

Eligible subjects who have signed an informed consent form (ICF)/parental consent form and assent form, where applicable, will be enrolled and randomized 1:1 to a treatment sequence via an electronic system using a permuted-block schedule stratified by investigational site. Subjects will be randomized to receive either MIR RBCs followed by REF RBCs, or to receive REF RBCs followed by MIR RBCs.

The crossover trial design will consist of 2 treatment periods. Each period will include a 50-day wash-in phase (Day 0 of the wash-in = Day 0 of the treatment period) followed by 2 transfusion episodes for assessment of the primary endpoint. The 50-day wash-in serves to ensure that an adequate volume of RBCs from the assigned treatment allocation (MIR RBCs versus REF RBCs) have been transfused into the subject prior to collecting samples to support the primary endpoint.

An end of study treatment follow-up visit will occur 2-4 weeks after the last per protocol transfusion, which should coincide with the next standard of care transfusion. A final study visit will occur at least 60 days after the last per protocol transfusion.

During each treatment period, blood samples will be collected for safety and efficacy analysis.

Blinding is not feasible because riboflavin used in the Mirasol-treated WB may cause yellow colored urine in transfusion recipients of Mirasol-treated blood products. Also, there is a difference in MIR RBC and REF RBC storage bags and labels. However, subjects, investigational site staff, and the Sponsor will not be informed of the randomization assignment. Study team members conducting safety assessments on subjects should remain blinded, whenever possible, to ensure causality determination remains unbiased. Central and Local Blood Centers will be informed of the randomization assignment to provide study product for transfusion.

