### **A. Adverse Events**

All subjects will be assessed regularly for potential occurrence of adverse events (AE) from the treatment period until the subject is off study. The Medical Dictionary for Regulatory Activities (MedDRA; Version 16.1) will be used to code all adverse events to a System Organ Class (SOC) and Preferred Term (PT). The incidence of treatment-emergent AEs (TEAE) will be summarized and tabulated by treatment group. A TEAE is defined as any AE that occurs on or after the date of first transfusion.

The National Cancer Institute Common Terminology Criteria for Adverse Events (version 4.03; CTCAE) will be used to grade severity of all AEs. The severity of each AE will be assessed as mild, moderate, severe, life-threatening or fatal. Several occurrences of the same AE in one subject will be counted once and the one with worst severity will be counted.

The relationship of each AE to the study treatment or to study procedure will be grouped as related or unrelated. Any AE with a CRF description of definitely related, probably related, or possibly related will be considered related. Any AE

with a CRF description of not related will be considered unrelated. Several occurrences of the same AE in one subject will be counted once and the one with the closest relationship to study treatment or to study procedure will be counted. If an AE is missing the relationship to study medication, the event will be assumed to be related for analysis and summarization.

The number and percentage of patients reporting each PT will be summarized by the treatment received in the period of onset. Incidence of AEs by maximum reported CTCAE grade will also be tabulated within each arm. The SAEs and AEs leading to study discontinuation will be displayed. The following summaries will be presented:

- Overall summary of TEAEs
- TEAEs by SOC and PT. The number and percentage of subjects with at least one TEAE, as classified by system organ class (SOC) and preferred term (PT), will be summarized by treatment received in the period of onset. For these summaries, subjects with multiple events will be counted only once per SOC and preferred term.
- Study Treatment-related TEAEs by SOC and PT
- Study Procedure-related TEAEs by SOC and PT
- TEAEs by maximum CTCAE grade, SOC and PT
- Serious TEAEs by SOC and PT
- UADEs by SOC and PT
- Adverse transfusion reactions
- TEAEs causing discontinuation from the study
- All-cause mortality

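### The SAP's partial-date rule for adverse events takes no account of the two treatment periods, so an imputed onset can credit an event to the wrong product

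*SAP*

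**What the plan says.** SAP VI.B (Missing Data) has separate bullets for partial AE onset dates:

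- **Day missing, month of first dosing.** The rule applies "where the month and year correspond to the first day of dosing the day will be imputed to the first day of dosing".
- **Day missing, any other month.** "All other missing days will be imputed to 15". The same sentence also closes the bullets for other dates; the one in the AE-onset bullets is meant here.
- **Month and day missing, year of first dose.** "if the year corresponds to the year of first dose, the date will be imputed as the same as the date of first dose".
- **Month and day missing, any other year.** "Otherwise, the month will be imputed to 7 and the day will be imputed to 15".

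First dose and first day of dosing are not defined. Nothing in these bullets mentions the start of Period 2, the AE stop date, the visit at which the event was recorded, or the last visit.

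Elsewhere the SAP is organised by period. Under Design Overview, "The crossover trial design will consist of 2 treatment periods". Under Study Time Points, "Treatment start date is defined within each period as the date of the first transfusion received for each period". SAP IX.A then tabulates AEs by period: "The number and percentage of patients reporting each PT will be summarized by the treatment received in the period of onset". Protocol 21.9.1 says the same. Treatment-emergent status has only a lower limit: "A TEAE is defined as any AE that occurs on or after the date of first transfusion".

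**The concern.** In a parallel-group trial the imputed onset mainly settles whether an event is treatment-emergent. In this crossover it also settles the product. A rule that does not look at the crossover date can move a Period 2 event into Period 1, or the reverse.

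Comparing safety between treatments is a secondary objective (Protocol 7.2, SAP II.B). In the REF-then-MIR sequence, an event moved back to Period 1 is taken off the investigational product. In the MIR-then-REF sequence, the same move charges a REF event to MIR. With 1:1 allocation to sequence, such mixing tends to dilute a real difference between products, which is undesirable in a safety table.

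**Working it through.** **Timeline.** Inputs: mean transfusion intervals of 2-4 weeks (Protocol 11.2), a 50-day wash-in followed by two episodes per period (10.1), and a final visit at least 60 days after the last study transfusion (10.4). Assumptions: a constant interval, Period 2 starting one interval after the second endpoint episode, and the final visit at exactly 60 days.

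| Interval | Endpoint episodes (day) | Period 2 starts | Last study transfusion | Final visit |
|---|---|---|---|---|
| 14 days | 56, 70 | 84 | 84 + 70 = 154 | 214 |
| 21 days | 63, 84 | 105 | 105 + 84 = 189 | 249 |
| 28 days | 56, 84 | 112 | 112 + 84 = 196 | 256 |

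Dividing by 30.4375 (Protocol 21.2) gives 7.0, 8.2 and 8.4 months, or 8.0, 9.1 and 9.3 with 28 days of screening. This agrees with the stated 7-9 months.

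The AE-onset rule was then applied to every onset day from first transfusion to final visit, for every start date in a 365-day year. The anchor was read in two ways: (a) the first study transfusion; (b) the first transfusion of each period. The main results can also be checked by hand.

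**Day missing, crossover month, reading (a).** Let Period 2 start on day c of a month with M days. Every day-missing onset in that month becomes the 15th.
- If c ≤ 15, the c − 1 earlier days are wrongly put in Period 2. Summed over c: 0 + 1 + … + 14 = 105.
- If c > 15, the M − c + 1 later days are wrongly put in Period 1. Summed over c for M = 30: 15 + 14 + … + 1 = 120.
- M = 30: (105 + 120)/900 = 25.0%. M = 31: (105 + 136)/961 = 25.1%. M = 28: (105 + 91)/784 = 25.0%.

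Across all months, 3.0-3.5% of day-missing onsets change product and 1.3-1.6% land after the final visit.

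**Day missing, crossover month, reading (b).** Every such onset becomes day c, so the c − 1 earlier days move from Period 1 to Period 2 and none move back. The share is (M − 1)/(2M): 29/60 = 48.3% for M = 30 and 48.4% over the year. Across all months, 5.7-6.8% change product.

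**Month and day missing, reading (a).** A Period 2 onset in the calendar year of the first dose is set to that dose, so it moves to Period 1. For an onset k days after the first dose, the share of start dates that leave it in the same year is (365 − k)/365. Averaged over Period 2:
- 14 days: 1 − [(84 + 214)/2]/365 = 1 − 149/365 = 59.2%
- 21 days: 1 − 177/365 = 51.5%
- 28 days: 1 − 184/365 = 49.6%

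Over both periods, 33.2-37.8% of such onsets change product and 20.4-24.4% land after the final visit.

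**Month and day missing, reading (b).** The text does not say which start applies when both fall in one year. Taking the earlier gives the same 49.6-59.2% of Period 2 onsets moved; over both periods, 34.6-40.5% change product and 10.9-11.4% land after the final visit.

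**Examples, 3-week interval.**
- First transfusion 10 January, Period 2 starts 25 April. An onset on 28 April with the day missing becomes 15 April under (a), which is Period 1. An onset on 10 April with the day missing becomes 25 April under (b), which is Period 2.
- First transfusion 1 October 2018, final visit 7 June 2019. Under (a), a February 2019 onset known only by year becomes 15 July 2019, 38 days after the final visit.

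**The case against.** **The anchor may be per period.** SAP VI.A defines study day and treatment start within each period, just before this rule. A reader might infer that only the start of the study is protected, so that an event after a Period 2 start on the 20th must be dated the 15th and charged to Period 1. The documents do not establish that: on the per-period reading this case cannot occur, and crossover-month errors run the other way. This stands. It does not rescue the rule, because both readings misassign events.

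**Few dates will be partial.** AEs are recorded before, during, one day after and seven days after each transfusion (Protocol 14.3), and Protocol 22.2.2 requires missing data to be explained. An onset known only by year should be rare. This also stands; the documents give no rate of partial dates.

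**Attribution near the switch is blurred anyway.** There is no washout. Mean linear red cell survival in IMPROVE II was 60.49 days (Mirasol) and 81.57 days (control) (Protocol 5.2), so both products circulate around the crossover. The tables are descriptive, and no safety test is planned. This limits the consequence for events close to the switch. It does not cover a year-only onset moved from Period 2 to the first day of the study.

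**A date after the last visit may do no harm.** A reader might infer that such events drop out of the tables. They do not, because the treatment-emergent definition has no upper limit. The fault there is an impossible date, not a lost event.

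**Conclusion.** The concern holds as a minor defect: on either reading of the anchor, the written rule can credit an event to the wrong product. The clause for missing month and day has the higher error rate; the day-15 default changes product only in the crossover month.

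It would go too far to call crossover-month assignment arbitrary under the first-study-transfusion reading: about three in four of those onsets still go to the right product. All percentages are conditional on a partial date and rest on evenly spread onsets and start dates. The number of events affected is probably small.

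Treatment-emergent status does not change, since every imputed date is on or after the first study transfusion. The primary endpoint does not use AE dates.

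The calculations end AE recording at the final visit (Protocol 19.6.1). Protocol 21.9.1 and SAP IX.A also describe it as ending at the end of study treatment follow-up visit. With that earlier limit, more imputed dates would fall after the window.

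**What to change.** Rewrite the AE-onset bullets in SAP VI.B:

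1. Define the anchor as the first transfusion of the relevant treatment period.
2. Assign the period first, from the known parts of the onset date, the AE stop date and, where the eCRF holds it, the visit at which the event was first recorded.
3. Impute the onset within that period, and never after the AE stop date or the subject's last visit. If a default such as the 15th or 15 July falls outside these limits, move it to the nearest date inside them.
4. If the period cannot be determined, count the event under MIR RBCs. This follows the SAP's own conservative conventions: an AE with missing relationship is taken as related (VI.B), and a period with any MIR RBC exposure is classed as MIR in the Safety Set (VI.I).

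The cost is a few sentences in the SAP and a small change to the date-derivation program, with no new visit, sample or test. There are two caveats. A few unclear REF events may be counted against MIR. The sponsor must also confirm that the eCRF captures the visit of first recording: the protocol mentions AE pages but does not say that they hold it. If they do not, step 2 rests on the date parts and stop date alone, and more events will fall to step 4.

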### **C. Multiple Study Centers**

No adjustment for stratification by the study centers is planned. However, centers will be grouped by region (US vs. non-US) and a sensitivity analysis will be conducted to determine if region impacts the primary endpoint.

### **D. Covariate Adjustment in Primary Analysis**

Pre-transfusion Hb level will be included as a covariate in the primary analysis.

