21.7.1 Endpoint Measures

21.7.1.1 Primary Endpoint

The primary endpoint is normalized Hb AUC as a measure of the percent surviving RBCs. The Hb AUC is calculated using the trapezoidal method on normalized Hb. The normalization is accomplished by dividing all posttransfusion Hb values by the 15-minute posttransfusion Hb level. The ratio is expressed as a percentage. A natural log-transform of the observed normalized Hb AUC will be utilized.

The Hb will be collected within 1 hour before transfusion, 15 (+ 5) minutes, 24 ± 6 hours, and 7 days after transfusion and at the end of study treatment follow-up. The transformed Hb AUC values from the first 2 transfusion episodes after the 50 day wash-in for each period will be used for analysis. If only a single Hb AUC value is available after the wash-in for an individual period, that single value will be used for analysis.

If a patient randomized to receive RBCs derived from Mirasol-treated WB in a particular period receives 2 successive off-protocol transfusions (ie, untreated RBCs) after completing the 50 day wash-in period, the primary endpoint for that period will be excluded from the analysis. If only 1 of the 2 successive transfusions after the 50 day wash-in period is per protocol, only the primary endpoint associated with the per protocol transfusion will be analyzed.

The primary analysis will use a mixed effect repeated measures model on the log-transformed data to assess differences between treatments using the FAS. A random subject-level effect will be used to accommodate dependence in responses within subjects over time. Fixed main effect terms for period and carry-over will be modeled along with treatment, where Mirasol-treated WB is coded 1 and conventional treatment is 0. A one-sided 97.5% confidence interval for treatment differences will be used to test the primary hypothesis that the normalized Hb AUC as a measure of RBC survival derived from Mirasol-treated WB is non-inferior to normalized Hb AUC after transfusion of conventional untreated RBCs. Assuming a non-inferiority margin of 20% (at the original scale), the use of RBCs derived from Mirasol-treated WB will be declared non-inferior to conventional, untreated RBCs if the lower limit of the one-sided confidence interval for the treatment effect (RBCs derived from Mirasol-treated WB mean minus conventional) is greater than $\ln(0.80) = -0.2231$.

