### **B. Primary Efficacy Endpoint Analysis**

The primary analysis will use a mixed effect repeated measures model on the log-transformed data to assess differences between treatments using the FAS. A

random subject-level effect will be used to accommodate dependence in responses within subjects over time. Fixed main effect terms for period, treatment, treatment\*period interaction and baseline normalized Hb AUC will be included in the model. Mirasol-treated WB will be coded as 1 and conventional treatment will be coded as 0 in the model.

A one-sided 97.5% confidence interval for treatment differences will be used to test the primary hypothesis that the normalized Hb AUC as a measure of RBC survival derived from Mirasol-treated WB is non-inferior to normalized Hb AUC after transfusion of conventional untreated RBCs. Assuming a non-inferiority margin of 20% (at the original scale), the use of RBCs derived from Mirasol-treated WB will be declared non-inferior to conventional, untreated RBCs if the lower limit of the one-sided confidence interval for the treatment effect (RBCs derived from Mirasol-treated WB mean minus conventional) is greater than  $\ln(0.80) = -0.2231$ .

The following provides sample code for implementing the MMRM analysis:

```
ods output lsmeans=lsmeans diff=diffs;
proc mixed data=test;
class subjid trt period trannum;
model resp=period trt trt*period trannum basehb/ddfm=kr;
random subjid(sequence)/sub=subjid type=cs;
lsmeans trt/diff alpha=.05;
```

where

- RESP is the log(normalized Hb AUC)
- TRT is the variable for treatment (0 for REF RBCs; 1 for MIR RBCs)
- BASEHB is the pre-treatment Hb
- PERIOD is the variable for period
- TRANNUM is the variable to identify the order of the two transfusions following the 50-day washin-in period for each treatment period (1 for first transfusion, 2 for second transfusion)
- SUBJID is for subject

The carryover effect will be tested with the TRT\*PERIOD interaction term. If the interaction is significant, then a carryover effect may be present and alternative analysis methods may be considered.

Several secondary/exploratory analyses will be conducted on the primary endpoint. Each are described below:

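### The SAP names conflicting covariates for its one confirmatory model: an Hb level whose sampling time is not settled, and a baseline normalized Hb AUC that cannot be computed before study product is given

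*SAP*

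**What the plan says.** The covariate for the primary analysis is described in three places in the SAP.

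- **VI.D (Covariate Adjustment in Primary Analysis):** "Pre-transfusion Hb level will be included as a covariate in the primary analysis". It does not say which transfusion or which period.
- **VIII.B, model text:** "Fixed main effect terms for period, treatment, treatment\*period interaction and baseline normalized Hb AUC will be included in the model". No Hb level is listed.
- **VIII.B, sample code and key:** "model resp=period trt trt*period trannum basehb/ddfm=kr", with the explanation "BASEHB is the pre-treatment Hb". No AUC term is fitted. The code also has TRANNUM, the order of the two evaluated transfusions, which the text's list of fixed effects leaves out.

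The general definitions in SAP VI.A apply to each treatment period: "Baseline for analysis purposes is defined as the last assessment prior to treatment start date/time", and "Treatment start date is defined within each period as the date of the first transfusion received for each period". Neither VI.D nor the code key refers to them.

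The protocol's primary model (21.7.1.1) has no Hb or AUC covariate: "Fixed main effect terms for period and carry-over will be modeled along with treatment".

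**The concern.** An Hb concentration and an area under a normalized Hb curve are different quantities. A statistician working from the VIII.B text and one working from the code would fit different models to the same confirmatory non-inferiority test.

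Timing matters as well as naming. In a crossover, a covariate measured after study product has been given can itself differ by product. Adjusting for it can then move the treatment estimate, in a test whose planned true effect lies only about 0.04 log units from the margin. The models for the 15-minute Hb and the actual Hb AUC (SAP VIII.C) follow the primary model and inherit the same ambiguity.

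**Working it through.** **1. The plan's own figure.** The inputs are in SAP IV.C: variance of within-subject differences 0.015412, a 16.7% reduction, margin ratio 0.80, one-sided alpha 0.025, power 80%.

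- Distance to margin: ln(0.833) − ln(0.80) = 0.04042.
- Normal approximation: (1.960 + 0.842)² × 0.015412 / 0.04042² ≈ 74.
- Noncentral t with n − 2 degrees of freedom: N = 77, as stated (n − 1 gives 76).
- Dropout: 77 / 0.80 = 96.25, so 97 randomized.

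The printed log mean of −0.1839 would give 81, with 78.2% power at 77. That is a separate matter. The calculation has no covariate term, so it does not indicate which covariate was meant.

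**2. Can a baseline normalized Hb AUC exist?** By SAP VI.B and VIII.A, an AUC needs the 15-minute post-transfusion Hb, the closing value, and at least one of the 24-hour and Day 7 values. Under Protocol 14.3 and Table 14-1 these samples start with the first study transfusion, and no CBC is scheduled at screening. No AUC that precedes study product can therefore be computed from scheduled data. The AUCs available before the evaluated episodes are the wash-in AUCs, which follow study product. The imputation paragraph of VIII.B lists wash-in AUCs and pre-transfusion Hb level as separate variables, so the SAP itself treats them as distinct.

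**3. Which Hb?** Hb is drawn before every transfusion (Protocol 14.3.1).

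| Reading | Basis | What precedes the value |
|---|---|---|
| One Hb per period | BASEHB with the VI.A baseline rule | Period 1: no study product. Period 2: a full period on the other product |
| Hb before each evaluated episode | VI.D read literally | At least 50 days on the assigned product |
| One Hb before the first Period 1 transfusion | Stated nowhere | No study product |

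For the first row, a full period is nominally 50 + 2×14 = 78 to 50 + 2×28 = 106 days, using the 2-4 week intervals of Protocol 11.2. It is longer if the first evaluated transfusion falls after Day 50.

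**4. What adjustment could do, in symbols.** Let b be the fitted slope of log AUC on the covariate, and δ the MIR minus REF difference in pre-transfusion Hb caused by product. The adjusted estimate equals the unadjusted one minus b times the mean MIR-minus-REF difference in the covariate. Take 1:1 sequences and complete data.

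- Per evaluated episode: the covariate difference is δ, so the shift is −bδ.
- Per period: in sequence MR the difference is initial Hb minus Hb after MIR. In RM it is Hb after REF minus initial Hb. On average this is −δ/2, so the shift is +bδ/2.
- One Hb per subject: the difference is 0 for every subject, so the shift is 0.

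For equal b and δ, the first two readings push in opposite directions. The documents give neither b nor δ, so the algebra shows that the choice can matter but not by how much.

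**The case against.** The strongest reply is that the SAP nearly settles the matter. BASEHB is the only implemented variable, its key speaks of treatment rather than transfusion, and VI.A defines baseline per period. Together these point to one Hb per period, and the AUC phrase looks like a drafting slip. SAP I.B also requires changes to the SAP to be made by a blinded statistician before lock. Most of this stands: it would be too strong to say that the SAP gives no time point at all, and the per-episode reading is the less supported one. But the SAP has no rule that code overrides text, the blinding rule does not say which covariate governs, and the per-period value in Period 2 still follows study product.

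Three stronger readings are tempting and are not supported.

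- **That type I error or power is materially wrong.** This needs the product difference in pre-transfusion Hb, its relation to log AUC within subjects, and its relation between subjects, none of which the documents give. One assumed case shows how little can be concluded: per-episode Hb, within-subject correlation 0.3, MIR Hb lower by half a within-subject SD. A paired-difference analysis gives a type I error of about 15%. A random-subject model with no between-subject slope gives about 5-8%. If pre-transfusion Hb does not differ by product there is no shift, and that is possible because physicians set volume and frequency.
- **That the second-episode Hb is part of the outcome it adjusts.** It is the "end of transfusion interval (ie, pre-transfusion measure for the subsequent interval") of the first evaluated AUC. It would adjust the second AUC, so its weight in the first quantifies no bias in the treatment contrast.
- **That the protocol and SAP contradict each other because the protocol model has no covariate.** Protocol Section 21 says that it summarizes the methods and leaves the SAP to follow, so this is not counted as a separate error.

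**Conclusion.** The point holds as a contradiction in the specification of the single confirmatory model, together with a timing problem. The covariate in the VIII.B text is either not computable before study product or, if wash-in AUCs were meant, measured after it. The Hb in VI.D and the code is measured after study product for at least part of the data under both available readings. Whether this would bias the result, and in which direction, cannot be determined from the documents.

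The conclusion rests on the sampling schedule and the definitions as written and needs no assumed effect size. It should be corrected before database lock because it affects the primary test and the correction is simple.

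**What to change.** Before database lock, in the SAP:

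1. Delete the baseline normalized Hb AUC from the VIII.B model text.
2. Name one covariate identically in VI.D, the VIII.B text and the code key: the Hb taken within 1 hour before the first Period 1 transfusion, one value per subject, used in both periods. Protocol 14.3.1 already collects it. Alternatively, use no covariate, as in Protocol 21.7.1.1, and remove BASEHB from the code and VI.D.
3. Report any model that uses a later Hb as a sensitivity analysis only.
4. Apply the same rule to the 15-minute Hb and actual Hb AUC models in VIII.C.
5. List TRANNUM in the VIII.B text, as in the code.

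The cost is wording only. N = 77 (97 randomized) is unchanged because the calculation uses no covariate. With complete data a subject-constant covariate leaves the within-subject treatment contrast unchanged, so it neither gains nor loses power against having no covariate. With the planned 20% discontinuation some subjects may contribute one period only. Any effect of the covariate should then be small, though this was not calculated.
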